4.1.1. Part 1: Single and Multiple Ascending Dose in Healthy Participants

Part 1 is within-cohort randomized, participant- and investigator- blind, sponsor-open, and placebo-controlled investigation of the safety, tolerability, PK, and immunogenicity following SAD and MAD of PF-07242813.

Approximately 97 healthy adult participants will be enrolled at a single study site into the proposed cohorts listed below. Participants may only participate in one cohort.

Participants in the single dose cohorts will be randomized sequentially as follows:

- Cohort 1 (n=4): 0.3 mg active (n=2) or placebo (n=2), IV;
- Cohort 2 (n=4): 1 mg active (n=2) or placebo (n=2), IV;
- Cohort 3 (n=4): 3 mg active (n=2) or placebo (n=2), IV;
- Cohort 4 (n=8): 10 mg active (n=6) or placebo (n=2), IV;
- Cohort 5 (n=8): 30 mg active (n=6) or placebo (n=2), IV;
- Cohort 6 (n=8): 100 mg active (n=6) or placebo (n=2), IV;
- Cohort 7 (n=8): 300 mg active (n=6) or placebo (n=2), IV;
- Cohort 8 (n=8): 1000 mg active (n=6), or placebo (n=2), IV.

Participants in the multiple dose cohorts, will be randomized as follows:

- Cohort 10 (n=8): 15 mg active (n=6) or placebo (n=2), SC x 3 doses Q2W;
- Cohort 11 (n=8): 50 mg active (n=6) or placebo (n=2), SC x 3 doses Q2W;
- Cohort 12 (n=8): 150 mg active (n=6) or placebo (n=2), SC x 3 doses Q2W;
- Cohort 13 (n=8): 300 mg active (n=6) or placebo (n=2), SC x 3 doses Q2W;
- Cohort 14 (n=8, optional): ≤ 1000 mg IV active (n=6) or placebo (n=2), SC x 3 doses Q2W.

The Japanese Participant Cohort will be randomized as follows:

- Cohort 15 (n=5): a single IV dose active (n=4) or placebo (n=1).

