Within 28 days of successful completion of the screening process, eligible participants will be randomized to receive a single IV infusion of PF-07242813 or placebo. In order to mitigate any unanticipated acute safety risks within the IV infused SAD cohorts, sentinel dosing will be implemented in all SAD cohorts (ie, cohorts where the dose being tested is the highest administered in the study to date). For sentinel dosing, the first 2 participants (1 active: 1 placebo) will be dosed prior to the remaining participants in the cohort and monitored for at least 24 h to assess safety. If the dose level for the first 2 sentinel participants is determined to have an acceptable safety and tolerability profile, as judged by the investigator, the remaining participants within the cohort will be dosed. Single dose cohorts will be enrolled sequentially in a dose escalating fashion starting from the lowest proposed dose (0.3 mg). During the SAD period, escalation to subsequent dose levels will occur following the sponsor's review of available safety through study Day 8 and PK data through Day 3 for the previous cohort. There will be a minimum of 10 days between cohorts for dose escalation. Dosing in this part (up to the maximum dose of 1000 mg IV) may be adjusted depending upon the actual exposure of PF-07242813 observed in humans at lower doses. If, based on the observed data, the subsequent dose projected group mean C_{max} is $> 1020 \mu\text{g/mL}$ or $AUC_{168H} > 106000 \mu\text{g.h/mL}$, the exposure limits determined as 1/10th of the mean exposures observed at NOAEL in the 13-week cynomolgus monkey toxicity study, that dose will not be explored.

Participants will be admitted into the clinic approximately 1 day prior to dosing and be required to stay overnight in the study center through completion of Day 5 evaluations. Participants in the single dose cohorts will return for outpatient visits per the [Schedule of Activities \(Table 1\)](#), up to Day 71 visit (or at least 4 half-lives of PF-07242813 based on observed data). For Cohort 1, the outpatient visit is up to Day 29 (± 3 days). For Cohorts 2 and 3, the final out-patient visit will be determined based on emerging safety and PK data from previous cohort(s). As such, the final scheduled visit may be earlier than Day 71 (± 3 days), but will be at least through Day 29 (± 3 days).

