6.3. Measures to Minimize Bias: Randomization and Blinding

6.3.1. Allocation to Study Intervention

The investigator will assign participant numbers sequentially to the participants as they are screened for the study. Pfizer will provide a randomization schedule to the investigator and, in accordance with the randomization numbers, the participant will receive the study treatment regimen assigned to the corresponding randomization number. It will also appear on the study medication containers. Study intervention will be dispensed at the study visits summarized in the [SoA](#).

Healthy participants will be randomized (once) into the SAD period, at which time, they will receive treatment assignment (PF-07242813 or placebo) for both the SAD and MAD periods. Participants will receive the same blinded treatment assignment (ie, the same dose level of PF-07242813 or placebo) throughout, in both the SAD and MAD cohorts.

- The randomization ratio for the cohorts in the healthy participant SAD/MAD segment will be 3:1 (PF-07242813:Placebo) with the exception of Cohorts 1-3, which will be randomized 1:1.
- The overall randomization ratio for the atopic dermatitis cohorts will be 2:1 (PF-07242813:Placebo) for Cohort 9.

Investigators, all participants and all study personnel involved in the study, with the exception of the pharmacist who prepares the study treatment and, as needed, an individual designated to administer study intervention who has no other involvement with study conduct, personnel, or participants, will remain blinded to each participant's assigned study intervention throughout the course of the study. In order to maintain this blind, an otherwise uninvolved third party will be responsible for the preparation and dispensing of all study intervention and will endeavor to ensure that there are no differences in time taken to dispense or visual presentation following randomization.

In the event of a Quality Assurance audit, the auditor(s) will be allowed access to unblinded study intervention records at the site to verify that randomization/dispensing has been done accurately.

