6.3.2. Breaking the Blind

The method for breaking the blind in this study will be manual. A sealed envelope that contains the study intervention assignment(s) for each participant will be provided to the investigator. The sealed envelope will be retained by the investigator (or representative) in a secured area. In case of an emergency, the investigator has the sole responsibility for determining if unblinding of a participant's treatment assignment is warranted. Participant safety must always be the first consideration in making such a determination. If the investigator decides that unblinding is warranted, the investigator should make every effort to contact the sponsor prior to unblinding a participant's treatment assignment unless this could delay further management of the participant. If a participant's treatment assignment is unblinded, the sponsor must be notified within 24 hours after breaking the blind. When the blinding code is broken, the reason must be fully documented and entered on the CRF/DCT.

Once the study is complete, all envelopes (sealed and opened) must be inventoried and retained until authorization for destruction has been provided.

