6.6. Dose Modification

6.6.1. Dose Escalation and Stopping Rules (Part 1)

Dose escalation stopping rules will be used to determine whether the maximal tolerated dose has been attained. Dose escalation may be stopped if it is determined that the limits of safety and/or tolerability have been reached. This decision will be made after a discussion takes place between the sponsor study team and the investigator. The sponsor study team may not overrule the investigator's decision to stop dose escalation. If dose escalation is stopped because of any of these criteria, additional cohorts may receive the same or lower doses of the study intervention.

The dose escalation will be terminated based on the following criteria:

- If 50% or more of the participants receiving active drug at a given dose level (but not participants receiving placebo) develop similar clinically significant laboratory, ECG, or vital sign abnormalities, in the same organ class, indicating dose-limiting intolerance.
- If two-thirds of participants at a given dose level develop an individual participant stopping AE (see [Section 7.1](#)).
- Dosing will be paused for any SAE that occurs in a participant receiving active treatment until causality is fully assessed by the PI and sponsor. Dosing may resume if the SAE is determined to be not drug-related by the PI and sponsor. If the SAE is determined to be either drug-related or unknown, either dosing will cease or the SAE will be evaluated by the sponsor's protocol review committee (or similar review group), which is independent of the study team and investigators. If the protocol review committee determines that dosing may resume, a plan that mitigates risks to participants with the resumption of dosing will be implemented. Such a plan could include a revision of inclusion/exclusion criteria, repeating or reducing the dose, or adding appropriate safety monitoring.
- It is determined that the limit of safety and/or tolerability has been reached. This decision will be made following discussions between the study team and the investigator.
- Other findings that, at the discretion of the study team and investigator, indicate that dose escalation should be halted.
- If, at any dose level, the average exposure reaches or exceeds the PK stopping limits, C_{max} of 1020 μ g/mL and AUC_{168H} of 106000 μ g.h/mL

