9.5. Interim Analysis

No formal interim analysis will be conducted for this study. As this is a sponsor-open study, the sponsor may conduct unblinded reviews of the data during the course of the study for the purpose of safety assessments, facilitating dose-escalation decisions, PK/PD modeling, and/or supporting clinical development.

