- The investigator may change his/her opinion of causality in light of follow-up information and send an SAE follow-up report with the updated causality assessment.
- The causality assessment is one of the criteria used when determining regulatory reporting requirements.
- If the investigator does not know whether or not the study intervention caused the event, then the event will be handled as “related to study intervention” for reporting purposes, as defined by the sponsor. In addition, if the investigator determines that an SAE is associated with study procedures, the investigator must record this causal relationship in the source documents and CRF, and report such an assessment in the dedicated section of the CT SAE Report Form and in accordance with the SAE reporting requirements.

Follow-up of AEs and SAEs

- The investigator is obligated to perform or arrange for the conduct of supplemental measurements and/or evaluations as medically indicated or as requested by the sponsor to elucidate the nature and/or causality of the AE or SAE as fully as possible. This may include additional laboratory tests or investigations, histopathological examinations, or consultation with other healthcare providers.
- If a participant dies during participation in the study or during a recognized follow-up period, the investigator will provide Pfizer Safety with a copy of any postmortem findings including histopathology.
- New or updated information will be recorded in the originally completed CRF.
- The investigator will submit any updated SAE data to the sponsor within 24 hours

of receipt of the information.

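### The Part 1 SAE pause in Protocol Section 6.6.1 depends on the arm, and nothing keeps that signal from the blinded PI who helps decide whether dosing resumes

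*Protocol*

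**What the plan says.** Protocol Section 4.1.1 sets the blinding: "Part 1 is within-cohort randomized, participant- and investigator- blind, sponsor-open, and placebo-controlled investigation". Section 6.3.1 says that investigators and study personnel "will remain blinded to each participant's assigned study intervention throughout the course of the study"; the only exceptions are the preparing pharmacist and, where needed, a person who does nothing but give the dose. Section 9.5 confirms that the sponsor may look at unblinded data during the study.

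The stopping rules in Section 6.6.1 include this one: "Dosing will be paused for any SAE that occurs in a participant receiving active treatment until causality is fully assessed by the PI and sponsor". The next sentence gives the way out: "Dosing may resume if the SAE is determined to be not drug-related by the PI and sponsor". If the event is judged related, or the cause is unknown, dosing ceases or the case goes to a review group outside the study team and the sites.

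Appendix 3 (Section 10.3.3) requires the investigator to give a causality opinion before the SAE report first goes to the sponsor. It then adds: "The investigator may change his/her opinion of causality in light of follow-up information".

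Section 4.1.1 also describes sentinel dosing in the SAD cohorts: "the first 2 participants (1 active: 1 placebo) will be dosed prior to the remaining participants".

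**The concern.** A blinded PI cannot tell whether an SAE meets a condition that depends on the arm. Someone who knows the arm has to apply it, and the PI then sees whether dosing stopped. The same PI shares in the determination that lets dosing resume. As written, the pause can therefore tell the PI the arm just before, or while, the judgement that should be made blind is completed.

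The protocol closes a similar leak elsewhere: Section 8.5 withholds from sites any drug concentration data that could unblind. There is no counterpart for the SAE pause. Emergency unblinding under Section 6.3.2 is a separate, case-by-case decision of the investigator, and an SAE as such does not trigger it.

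Two things are at stake. One is the causality judgement used for resumption and escalation; Section 6.6.1 does not let the sponsor team overrule an investigator who decides to stop escalation. The other is later AE assessment in a participant whose arm has become known.

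**Working it through.** **1. Reproduce the allocation.** Cohort sizes are in Section 4.1.1 and totals in Section 9.2.1.
- SAD: 3 × (2+2) + 5 × (6+2) = 52, of whom 36 active and 16 placebo. This matches.
- MAD: 5 × (6+2) = 40, of whom 30 active and 10 placebo. This matches.
- With Cohort 15 (4+1), Part 1 is 97 = 70 active + 27 placebo.

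**2. What the PI knows before any pause.** Let p be the probability that the participant with the SAE is on active drug, taken from the allocation alone (assumption: an SAE is equally likely on either arm).
- Cohorts 1-3: 2/4 = 0.50. The sentinel pair is 1:1, so the remaining two are also 1:1.
- Any sentinel: 1/2 = 0.50.
- Non-sentinels in Cohorts 4-8: (6−1)/(8−2) = 5/6 = 0.83.
- MAD cohorts, which have no sentinel step: 6/8 = 0.75.
- Cohort 15: 4/5 = 0.80 (assumption: no sentinel pair, because Section 4.1.1 explains sentinel cohorts as those testing the highest dose to date).

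**3. What the pause adds.** Every SAE on active drug pauses dosing. Let q be the chance that dosing also stops after an SAE on placebo, for some other reason. Then:

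P(active | pause) = p / [p + (1 − p)q]

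P(active | no pause) = 0 for any q below 1, provided further dosing was due

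The literal rule is q = 0. The other values of q are assumptions that show the range; the documents give none. Example, MAD at q = 0.25: 0.75 / (0.75 + 0.25 × 0.25) = 0.92.

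| Participant | p | q = 0 | q = 0.05 | q = 0.25 | q = 0.50 | q = 1 |
|---|---|---|---|---|---|---|
| Cohorts 1-3, sentinels | 0.50 | 1.00 | 0.95 | 0.80 | 0.67 | 0.50 |
| MAD cohorts | 0.75 | 1.00 | 0.98 | 0.92 | 0.86 | 0.75 |
| Cohort 15 | 0.80 | 1.00 | 0.99 | 0.94 | 0.89 | 0.80 |
| Non-sentinels, Cohorts 4-8 | 0.83 | 1.00 | 0.99 | 0.95 | 0.91 | 0.83 |

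Only when pausing does not depend on the arm (q = 1) does the pause carry no information.

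**4. Spillover.** In a 1:1 sentinel pair, learning one arm gives the other. The same holds for the second pair in Cohorts 1-3. Among the six non-sentinels of Cohorts 4-8, a participant shown to be on placebo is the only one, so the other five are then known to be on active drug.

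**5. Is the signal visible?** It is when someone is waiting to be dosed. Part 1 runs at one site, MAD participants have three doses two weeks apart, and Cohort 10 starts after review of Cohort 6, so MAD dosing can overlap later SAD cohorts. An SAE on a SAD cohort's long follow-up can thus fall while others are due for dosing. After a sentinel event, the rest of the cohort is due.

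**6. Order of the causality opinions.** The first opinion precedes transmission to the sponsor (Section 10.3.3), so it is probably blind. The full assessment in Section 6.6.1 ends the pause and so is completed after the pause has begun; a revised opinion can come later still. No text says which of these governs resumption.

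**The case against.** The case against has several parts, and much of it limits the size of the problem.

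- **A pause is not proof of active drug.** Section 4.1.1 lets the investigator hold dosing after a sentinel event in either arm, and Section 6.6.1 allows discretionary halts. This stands, and is why the table runs over q. It weakens what a pause shows but leaves the no-pause signal intact.
- **No pause is often invisible.** If the whole SAD cohort has been dosed and the next one is waiting for its review, there may be nothing to pause. This stands; the 0% figure holds only when dosing was due.
- **A blind opinion already exists.** This stands for the first opinion. It does not settle the point, because nothing makes that opinion the one used for resumption.
- **The PI does not decide alone.** Resumption needs the sponsor's agreement too, and a related or unknown cause leads to cessation or outside review. If knowing the arm pushes the PI towards relatedness, the error is on the cautious side. When there is no pause, this bullet calls for no resumption decision. Both remarks stand and narrow the effect on dosing.

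A reader might infer that the primary safety endpoint is biased. The documents do not support that: the SAP (Sections 3.4.1 and 6.1.1.1.1) defines treatment emergence by start time, so a change in causality opinion alters no TEAE or SAE count. A reader might also take the 5:1 split of the remaining six in Cohorts 4-8 as something that an SAE reveals. It is fixed by the design before anyone is dosed. Nor is 75% the right starting figure for every 6:2 cohort; sentinel dosing makes it 50% or 5/6 in Cohorts 4-8.

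**Conclusion.** The point holds in a limited form. Section 6.6.1 is at odds with the blinding text in Sections 4.1.1 and 6.3.1: a rule that depends on the arm produces an action that the blinded PI can see, and the PI then shares in the decision that ends the pause.

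Under the literal rule, the PI's probability of active drug moves from 50%, 75%, 80% or 5/6, depending on cohort and sentinel status, to 100% or 0%. If up to half of placebo SAEs also led to a halt for other reasons, a pause would still leave it at 86% or more in the MAD cohorts, but at 67% where the starting value is 50%. These figures assume that SAEs are equally likely on both arms, that every SAE on active drug triggers the pause and, for the 0% figure, that dosing was due.

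The consequence is possible bias in SAE causality as used for resumption and escalation, and in later AE assessment for that participant. The documents do not show that such bias would be large, and they do not support any claim about incidence counts.

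**What to change.** Reconcile Section 6.6.1 with Sections 4.1.1 and 6.3.1 on three matters of blinding and record-keeping:

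1. Word the pause, or how it is communicated, so that what the site is told does not disclose the arm.
2. State that the PI's blinded causality opinion, which Appendix 3 already requires before the report is sent, is documented before any arm-dependent decision is communicated, and that it is the PI opinion used for resumption.
3. Record later revisions under Appendix 3 separately, noting whether the arm was known at the time. An absolute lock on the opinion would conflict with the right to revise it and is not suggested.

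The clinical content of the pause rule, including whether anything should follow an SAE on placebo, is for the sponsor to decide. The cost is one reworded bullet and slightly more documentation for each SAE.

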6.7. Intervention After the End of the Study

No intervention will be provided to study participants at the end of the study.

7. DISCONTINUATION OF STUDY INTERVENTION AND OF STUDY PARTICIPANT DISCONTINUATION/WITHDRAWAL

7.1. Discontinuation of Study Intervention

Note that discontinuation of study intervention does not represent withdrawal from the study. If study intervention is definitively discontinued, the participant will remain in the study to be evaluated for a minimum of 4 half-lives (approximately 70 days) after last dose. See the [SoA](#) for data to be collected at the time of discontinuation of study intervention and follow-up for any further evaluations that need to be completed.

In rare instances, it may be necessary for a participant to permanently discontinue study intervention (definitive discontinuation). Reasons for definitive discontinuation of study intervention include the following:

- Any participant who develops Grade 2 or higher adverse events for cardiac and blood/bone marrow categories and Grade 3 or higher adverse events in all other categories according to criteria defined in CTCAE, v. 5 will be discontinued from treatment, and followed until resolution of the adverse event(s).
- If a participant experiences symptoms typical of an allergic reaction, the study drug administration should be discontinued immediately and permanently;
- ECG changes (see below);
- Unacceptable toxicity;
- Pregnancy.

ECG Changes

A participant who meets the bulleted criteria based on the average of triplicate ECG readings will be withdrawn from the study intervention.

- QTcF >500 msec.

- Change from baseline: QTc >60 msec.

If a clinically significant finding is identified (including, but not limited to, changes from baseline in QTcF after enrollment), the investigator or qualified designee will determine if the participant can continue in the study and if any change in participant management is needed. This review of the ECG printed at the time of collection must be documented. Any new clinically relevant finding should be reported as an AE.

7.1.1. Temporary Discontinuation

If a participant experiences symptoms typical of infusion reactions (eg, lightheadedness, nausea, chills, fever), the study intervention infusion should be stopped. At the discretion of the investigator, the infusion can be restarted at a slower rate if symptoms are resolved within 1 hour after the stop of infusion. If symptoms return, then the study intervention administration should be discontinued immediately and permanently.

In the event that there is an infusion interruption, the entire duration of drug infusion, from the initial start of infusion to the completion of infusion, should not exceed 3 hours. The start and stop time of the infusion and the infusion rate and amount of volume infused in the event of an interruption will be recorded. Participants will receive appropriate treatment at the discretion of the investigator.

7.2. Participant Discontinuation/Withdrawal From the Study

A participant may withdraw from the study at any time at his/her own request. Reasons for discontinuation from the study include the following:

- Refused further follow-up;
- Lost to follow-up;
- Death;
- Study terminated by sponsor.

At the time of discontinuing from the study, if possible, an early discontinuation visit should be conducted. See the [SoA](#) for assessments to be collected at the time of study discontinuation and follow-up and for any further evaluations that need to be completed. The early discontinuation visit applies only to participants who are enrolled/randomized and then are prematurely withdrawn from the study. Participants should be questioned regarding their reason for withdrawal.

If a participant withdraws from the study, he/she may request destruction of any remaining samples taken and not tested, and the investigator must document any such requests in the site study records and notify the sponsor accordingly.

If the participant withdraws from the study and also withdraws consent (see [Section 7.2.1](#)) for disclosure of future information, no further evaluations should be performed and no additional data should be collected. The sponsor may retain and continue to use any data collected before such withdrawal of consent.

Lack of completion of all or any of the withdrawal/early termination procedures will not be viewed as protocol deviations so long as the participant's safety was preserved.

